There are 2 main challenges in applying diabetes prevention strategies to the population as a whole. Firstly, the lifestyle modification interventions employed in clinical trials are labour intensive and expensive (the US Diabetes Prevention Program^8, for example, cost over \$200million) and such trial-based interventions are unrealistic on a population level in any country. Secondly, the OGTT used to identify those in the population at high risk is a poorly reproducible and time-consuming test, both for the participant and for health care workers. More practical means of defining individuals who would benefit from lifestyle intervention are required.

We propose more practical solutions to these two issues. Firstly, our diabetes prevention strategy will employ a lifestyle modification programme delivered by text messaging in both India and the UK. Text messaging has been successfully used to modify behaviour in other contexts and the current proposal will assess the efficacy, acceptability and cost effectiveness of mobile phone based lifestyle intervention in IGR in India and the UK. The primary outcome will be progression to diabetes. Secondary outcomes will be physical activity, other cardiovascular disease (CVD) risk factors and quality of life. An economic analysis will be performed. Secondly, we propose to employ HbA1c measurement instead of the OGTT as the basis for intervention. This has the advantage of a single sample taken non-fasting. It reflects average circulating glucose levels over the preceding 4-8 weeks and has similar biological significance (in terms of the complications of diabetes) to that of OGTT glucose values. Since standardisation by the International Federation of Clinical Chemistry (IFCC), it has been recognised as a diagnostic test for diabetes by the American Diabetes Association (ADA), the European Association for the Study of Diabetes (EASD) and the International Diabetes Federation (IDF), with a cut-off at 6.5%. For impaired glucose regulation, the ADA has recommended the HbA1c range of 5.7-6.4%. International consensus has not yet been reached for IGR and we propose to use a range of 6-6.4% for recruitment into this study in both India and the UK to ensure that only patients at high risk are recruited. Baseline HbA1c has been found to be a better predictor of incident diabetes than the glucose values in the Indian population.

Specific objectives of the project are:

- To assess the efficacy in terms of progression to diabetes, and user acceptability, of a mobile phone-based lifestyle modification programme for people at risk of type 2 diabetes,

evaluating acceptable frequency and user selected content of the intervention in India and the UK

- to assess the effectiveness of such a lifestyle modification programme on change in objectively measured physical activity levels and on other CVD risk factors
- to assess the cost-effectiveness of this mobile phone-based lifestyle modification programme on the progression to diabetes and on improvement of the physical activity level over a 2 year period
- to develop and evaluate a pragmatic and scalable approach to identifying people at high risk of developing type 2 diabetes based on HbA1c in India.

Diabetes is projected to cause an estimated 4 million deaths globally in people aged between 20-79 years in 2010, which is equal to 6.8% of all expected deaths. The potential for lifestyle interventions to reduce the progression to diabetes from high risk states has been demonstrated in a number of RCTs in different countries, with a meta-analysis of RCTs suggesting that lifestyle intervention in high risk subjects can halve the incidence. The lifestyle modification RCTs showing reduced progression to diabetes in high risk subjects have given impressive results. They have however been expensive and labour intensive, with multiple personal contacts (including in some instances home visits) for those in the trial that were deemed to be failing to achieve their goals. Such intensive input is not practical on a large scale. Alternative methods to induce behavioural change, including contact via mobile phones or home computer, have been employed with success in other clinical situations.

A randomized controlled trial assessed 'Sweet Talk', a text messaging system designed to support young people with diabetes. Subjects aged between 8y and 18y were randomized to conventional therapy, conventional therapy and 'Sweet Talk' or intensive insulin therapy with 'Sweet Talk'. Conventional goal setting was reinforced by daily text messages containing personalized prompts and tailored messages. HbA1c only improved in subjects randomized to intensive therapy and 'Sweet Talk'. However 'Sweet Talk' was associated with improvements in diabetes self-management and self reported adherence; 82% of subjects felt that 'Sweet Talk' had improved their diabetes self- management and 90% wanted to continue to receive messages. In a recent meta- analysis of text messaging in the management of established diabetes (both type 1 and type 2), 22 trials covering 1657 participants were selected for review. Although criticisms could be made about publication bias, results from pooled data suggested that significant improvements in glycaemia and self-management were possible using mobile phone intervention.

Similar degrees of success and acceptability have been observed in other trials of the effectiveness of mobile telephone text messaging, for example as a reminder tool for improving adherence to sunscreen application and in a weight management programme in African American women. The proof of principle for lifestyle modification using text messaging interventions in other clinical situations has therefore been established.

In the UK, recruitment of high risk subjects will be from GP databases following HbA1c measurement as part of the NHS Health Checks and from routine screening of at-risk adults. NHS Health Checks, a cardiovascular risk assessment programme for all adults aged 40-74 years in England, was introduced in 2009 at an annual cost of £250 million. This

government-funded population-based programme aims to both accelerate overall reductions in CVD and diabetes incidence, and reduce known socio-economic and ethnic inequalities in cardiovascular health and diabetes. Delivered in primary care, the programme involves the systematic measurement of CVD risk factors and we shall select practices (the majority) in which HbA1c has been chosen as the indicator of glucose homeostasis.

The UK limb will be centred on a multi-ethnic population in London. There are 42,000 people eligible for the NHS Health Checks in this area. Between 8,000 and 14,000 people will be identified with IGR during the five year roll out of the National screening programme, that is between 1,600 and 2,800 people with IGR identified per year. Neighbouring areas in London will also participate as required.

**Potential risks and benefits** The potential risks and burdens for research participants are as follows:

At screening, visits 3,4 and 5 there is a venous blood test. These have the potential to cause discomfort. This will be minimised by experienced research personnel and appropriate use of equipment. The text messaging intervention may be irritating to subjects though the evidence base suggests that health interventions delivered in this way are welcomed. Subjects will be able to choose which day and which time of day they receive their messages to improve acceptability and minimise disruption.

The study requires minimal visits and only the randomisation and 6 month visits are over and above usual care for people at high risk of developing diabetes. All visits will be arranged according to subject preference for time and location.

The delivery of an education package for IGR at the start of the study for all participants is an advantage and is additional care above that usually delivered for people diagnosed with IGR.

The trial will be conducted in compliance with the protocol, GCP and the applicable regulatory requirement(s).

**Population to be studied** Subjects with impaired glucose regulation aged 18-74

**Trial Objectives and Purpose** This study assesses the efficacy, acceptability and cost-effectiveness of a text messaging system for delivering lifestyle advice to people with impaired glucose regulation.

**Trial Design** Subjects with impaired glucose regulation (defined as an HbA1c of 6.0-6.4%) will be randomised to usual care or usual care with text messaging. Text messages will be delivered three times weekly and will contain educational, motivational and supportive content on diet, physical activity, lifestyle and smoking. The content will be appropriate to the stage of the transtheoretical model of behavioural change that the subject is in (see appendices for transtheoretical model questionnaire, assessment scale and text messages). The primary outcome is progression to type 2 diabetes as defined by an HbA1c of 6.5% or over. Secondary outcomes are:

- Change in physical activity as measured by Actigraph and Recent Physical Activity Questionnaire (RPAQ)
- Change in weight, BMI, waist circumference, hip circumference and waist:hip ratio
- Change in fasting plasma glucose and HbA1c
- Change in lipid profile (total cholesterol, triglycerides, LDL cholesterol and HDL cholesterol)
- Liver function as measured by alanine transaminase (ALT), aspartate transaminase (AST) and gamma-glutamyl transferase (GGT)
- Change in diet assessed by validated food frequency questionnaire
- Quality of life assessed by EQ-5D questionnaire
- Acceptability of text message intervention assessed by questionnaire
- Cardiovascular biomarkers including hsCRP, adiponectin, PAI (plasminogen activator inhibitor), uric acid, white cell count, albumin, IL-6, IL-1, TNF- $\alpha$ , monocytes chemotactic protein-1, leptin, resistin, endothelin-1, E-selectin, soluble vascular cellular adhesion molecule-1 (sVCAM-1) and soluble interstitial cellular adhesion molecule-1 (sICAM-1)
- Insulin secretion and sensitivity

Lifestyle modification targets in the study are in line with previously published type 2 diabetes prevention studies:

1. A minimum of 150 minutes moderate intensity exercise per week
2. A minimum of 7% weight loss or achievement of a BMI of 25kg/m^2 (23kg/m^2 in South Asian subjects)
3. Less than 30% of total Kcal intake from fat
4. Less than 10% of total Kcal intake from saturated fat
5. Greater than 15g fibre per 1000Kcal intake

[figure not shown]
**Methodology** Randomised, controlled trial.

**Timescale** It is anticipated that the study will take 3 years with each subject being enrolled for 2 years with a total of 5 visits in that period.

**Population** n=2268 across the UK and India. n=1134 in UK sites randomized equally to 2 groups of 567.

Recruitment will be undertaken in both primary and secondary care targeting people with impaired glucose regulation (IGR). Identifying this group of people will be done by searching existing pathology databases held in NHS laboratories or GP records for fasting plasma glucose, HbA1c or an oral glucose tolerance test. These glycaemic measurements are done as part of the NHS Health check programme or other routine screening and are performed in NHS hospital labs. Access to the record of laboratory results will be done by only authorised personnel in the pathology department. Potential participants meeting the inclusion criteria for the study will be sent letters of invitation by the study team. Existing samples will not be used in the study. In addition, adverts and face to face talks to potential participants can be used where appropriate. An invitation letter and a participant information sheet together with a reply slip will be sent to potential participants. Those who have shown interest in the reply slips are encouraged to ask questions about the study. Only those who have agreed to take

part will be invited for screening. Informed consent will be taken before conducting any study procedures. During screening, glycaemic status will be confirmed with an HbA1c.

No concomitant medical therapies are contra-indicated. All study visits will take place in a local clinic at one of NHS research collaborating sites for the study.

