### **Efficacy**

The primary outcome will be progression to type 2 diabetes as measured by FPG (Fasting Plasma Glucose) or HbA1c at visits 3, 4 and 5 or by any validated criteria in any other care setting. The WHO/IDF criteria for diagnosis of diabetes will be used throughout.

1. If participant presents symptoms of diabetes and, FPG (Fasting Plasma Glucose)  $\geq 7.0$  OR HbA1c  $\geq 48$  then no repeat test is needed. The participant is diabetic.
2. If the participant does not present symptoms of diabetes;
  - If FPG  $\geq 7.0$  and HbA1c  $\geq 48$  then repeat both tests after 4 weeks. If the repeat results are FPG  $\geq 7.0$  or / and HbA1c  $\geq 48$ , the participant is diabetic.
  - If FPG  $< 7.0$  and HbA1c  $\geq 48$  then repeat HbA1c after 4 weeks. If the second result is  $\geq 48$ , the participant is diabetic.
  - If FPG  $\geq 7.0$  and HbA1c  $< 48$  then repeat FPG after 4 weeks. If the second result is  $\geq 7.0$ , the participant is diabetes.

Secondary outcomes will be:

- Change in physical activity as measured by Actigraph and Recent Physical Activity Questionnaire (RPAQ)
- Change in weight, BMI, waist circumference, hip circumference and waist:hip ratio
- Change in fasting plasma glucose and HbA1c
- Change in lipid profile
- Liver function as measured by alanine transaminase (ALT), aspartate transaminase (AST) and gamma-glutamyl transferase (GGT)
- Change in diet assessed by validated food frequency questionnaire
- Quality of life assessed by EQ-5D questionnaire
- Cardiovascular biomarkers including hsCRP, adiponectin, PAI (plasminogen activator inhibitor), uric acid, white cell count, albumin, IL-6, IL-1, TNF- $\alpha$ , monocytes chemotactic protein-1, leptin, resistin, endothelin-1, E-selectin, soluble vascular cellular adhesion molecule-1 (sVCAM-1) and soluble interstitial cellular adhesion molecule-1 (sICAM-1)
- Insulin secretion and sensitivity as calculated from fasting plasma glucose and insulin measurements

**Safety** Adverse events will be reported to the REC, the sponsor and the Principal Investigator immediately. Subjects will be followed-up after one week following an adverse event and thereafter in the clinically indicated follow up setting.

**Statistics** Missing, unused, and spurious data will be assessed on an individual basis and may be ignored, withdrawn or the visit may be removed from the analysis with appropriate justification adjudicated by the Principal Investigator.

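### The protocol states the primary outcome in two ways that disagree, so the same participant can be an event under one and not under the other

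*Protocol*

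**What the plan says.** Two sections of the protocol define the primary outcome.

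- **Trial Design:** "The primary outcome is progression to type 2 diabetes as defined by an HbA1c of 6.5% or over". No visits, second test, repeat or outside diagnosis are mentioned.
- **Efficacy:** progression is judged "as measured by FPG (Fasting Plasma Glucose) or HbA1c at visits 3, 4 and 5", "or by any validated criteria in any other care setting". If symptoms are present and either test is raised, "then no repeat test is needed". Without symptoms, an isolated raised HbA1c leads to "then repeat HbA1c after 4 weeks" and an isolated raised FPG to "then repeat FPG after 4 weeks". If both are raised, both are repeated, and one raised repeat is enough. The section adds that WHO/IDF diagnostic criteria apply throughout.

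Three other places bear on this. Subject inclusion criteria equate 6.0-6.4% with 42-47 mmol/mol. Subject exclusion criteria rule out FPG of 7.0 mmol/l or more at entry. Subject withdrawal criteria remove a participant immediately on a validated diagnosis of type 2 diabetes in any setting, and point to Efficacy for details of that diagnosis.

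**The concern.** The primary outcome rule decides who counts as an event, and so the event count, the event times and the estimated effect. Here the protocol gives two rules. Neither section refers to the other as the governing definition. If both stay in force, the definition used for the primary analysis could be chosen after both results are known.

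This is not detail that an analysis plan would normally supply. The protocol itself fixes the outcome twice, and an analysis plan should not have to choose between two endpoints in its parent document.

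The withdrawal rule sharpens the problem. A participant diagnosed through FPG or in another care setting leaves the study at once. Under Trial Design that participant is not an event, and the later trial HbA1c that could have made them one may never be taken.

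**Working it through.** **Is the threshold itself in conflict?** No. With 6.4% paired with 47 mmol/mol in the inclusion criteria, the next reportable values are 6.5% and 48 mmol/mol. The disagreement lies elsewhere.

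**Case-by-case comparison.** Trial Design is read literally: any HbA1c of 6.5% or over counts. HbA1c is in mmol/mol and FPG in mmol/l.

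| Case | Trial Design | Efficacy |
|---|---|---|
| 1. No symptoms; HbA1c ≥48, FPG <7.0; repeat HbA1c <48 | event | no event |
| 2. No symptoms; HbA1c ≥48 and FPG ≥7.0; both below the limits on repeat | event | no event |
| 3. No symptoms; FPG ≥7.0 on test and repeat; HbA1c <48 | no event | event |
| 4. Symptoms; FPG ≥7.0; HbA1c <48 | no event | event |
| 5. Outside diagnosis; no trial HbA1c ≥48 | no event | event |
| 6. HbA1c ≥48, confirmed or with symptoms | event | event |

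Cases 3 to 5 need no assumption about confirmation: Trial Design names HbA1c only. Cases 1 and 2 depend on reading its silence on repeat testing as meaning that none is required. On that reading neither definition contains the other, so counts can differ in both directions.

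**Can the stated sample size show which definition was meant?** The Population paragraph gives 2 × 567 = 1134 for the UK and 2268 in total, which equals 2 × 1134. The protocol states no event rate, effect size, power or significance level, so the figures cannot be traced to either definition.

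**How large is the difference?** The protocol has no inputs for this. As an illustration only, one simulation assumed:

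- within-person coefficient of variation 1.5-3% for HbA1c and 4-7% for FPG;
- mean HbA1c drift 0.5-1.5 mmol/mol per year;
- 0-10% with symptoms at a visit;
- HbA1c-FPG correlation 0.2-0.5;
- no outside diagnoses.

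With Trial Design read literally, 25-49% of participants were events over two years, against 21-44% under Efficacy. Events under Trial Design only made up 3.7-10.8% of participants, and events under Efficacy only 0.6-2.1%. Within single scenarios the ratio of event rates ran from 0.459/0.436 = 1.05 to 0.299/0.207 = 1.44. A second simulation on other assumed values gave 19-40% against 13-26%, with ratios of 1.3 to 2.0. The spread from 1.05 to 2.0 comes from the choice of assumptions.

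**The case against.** The best counter-reading is that the Trial Design sentence is a short summary, not a rival definition. It gives a threshold and is silent on visits and repeats. Efficacy has the visits, the algorithm and the statement that WHO/IDF criteria apply throughout, and the withdrawal criteria refer to it for details.

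Part of this stands. Trial Design does not rule out confirmation; it does not mention it. A rule of one unconfirmed HbA1c at any visit is written nowhere, so cases 1 and 2 are a literal reading and not a stated intention. But the summary reading does not remove cases 3 to 5. The sentence says how the outcome is defined, and names HbA1c alone. The pointer in the withdrawal criteria concerns withdrawal, not the primary analysis.

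Three stronger inferences are tempting and are not supported.

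- **That a single reading is mostly noise.** Entry lies directly below the cut-off, so a reader might compute chance crossings. For a stable true HbA1c of 6.3% and an assumed within-person SD of 0.15, the chance per visit of reaching 6.5% is 1 − Φ(0.20/0.15) = 0.091. Over three visits that gives 1 − (1 − 0.091)³ = 0.25, or 1 − (1 − 0.091²)³ = 0.025 if each crossing must be confirmed. If values from 6.45% round up to 6.5%, the figures become 0.40 and 0.07. With the cut-off at 6.5%, SDs of 0.10 to 0.20 move the unconfirmed figure from 0.07 to 0.40. The protocol gives no SD, so none of these is a property of the trial.
- **That unconfirmed events fall equally in both arms and cost power.** In a simple HbA1c model (SD 0.15, no mean drift, cut-off 6.45%, FPG omitted) with an assumed treatment shift of −0.05 percentage points per year, unconfirmed-only events were about 10.7% in control and 8.8% on treatment. The risk ratio was weaker without confirmation (about 0.72 against 0.63), but the risk difference was larger (about 6.5 against 4.7 points). The z value at 567 per arm was about the same (2.7 against 2.6).
- **That Efficacy is a fully confirmed endpoint.** Participants with symptoms and those diagnosed elsewhere need no trial repeat.

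**Conclusion.** The protocol is wrong as written: two current sections define the primary outcome differently, and nothing states which governs the primary analysis. Two routes (FPG without raised HbA1c, and outside diagnosis) are events under Efficacy only, on any reading. An HbA1c of 48 or more that is not confirmed on repeat is an event under Trial Design only if that section is taken literally.

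A reader might infer that the trial will have two different primary results. The documents support only that it can: the two analyses might agree in their conclusion. Neither the size nor the net direction of the difference can be derived from the protocol. The conclusion therefore rests on the wording and the case comparison, not on any simulated figure. It must be corrected because it concerns the rule that generates the primary result.

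**What to change.** Reconcile Trial Design and Efficacy so that one definition governs the primary analysis and reads the same in both places. For example, the Trial Design sentence could refer to the single governing definition. Check that definition against the Subject withdrawal criteria, so that a diagnosis that ends participation has a clear status in the primary outcome. Keep the other definition only as a named sensitivity analysis. Which diagnostic rule should govern is for the investigators and sponsor to decide and is not judged here.

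The cost is one sentence in a protocol amendment, with no new data.

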### Visit 1: Screening

- Attend fasting
- Routine clinical examination including measurement of height, weight, waist circumference, hip circumference
- Measurement of blood pressure and heart rate
- 15mL (approximately 3 tablespoons) of venous blood taken for glucose, HbA1c, lipids, Creatinine, ALT, AST, GGT, insulin, cardiovascular biomarkers and serum save
- Urine pregnancy test in female subjects of childbearing age
- Random urine sample for microalbumin:creatinine ratio
- EQ-5D, RPAQ, TTM and food frequency questionnaires completed
- Actigraph physical activity monitor fitted according to manufacturer's instructions and worn for 7 days. Pre-paid addressed envelopes will be provided for the return of the Actigraph device or subjects may return them to the clinic.

### Visit 2: Education and Randomisation

- Delivery of structured education for IGR including:
  - Define IGR
  - Implications of IGR in progression to diabetes
  - Prevention of type 2 diabetes
  - Healthy lifestyle advice
  - Dietary advice
  - Physical activity advice

- Written material given (see appendix)
- Randomised to control (usual care) or text message arm with randomisation minimised by gender and age in decades.

